2.3 Correlative Research

- 2.31 To assess the immune response to pneumococcal vaccination as measured by fold-change from pre-vaccine (day 15) to 28 days post-vaccination in opsonophagocytic activity (OPA) GMT of antibodies from sera.
- 2.32 To assess the immune response to pneumococcal vaccination as measured by fold-change from pre-vaccine (day 15) to 28 days post-vaccination in quantitative *Streptococcus pneumoniae* immunoglobulin G (IgG) GMT of antibodies from sera.
- 2.33 Evaluate the effect of 6 weeks of low dose lenalidomide on global immune function including T-cell repertoire, T-cell immune synapse, serum immunoglobulin levels, and absolute numbers of T-cell and NK cells.

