16.0 Statistical Considerations and Methodology

16.1 Overview:

This is a randomized Phase II study designed to compare the response rate of the control arm (Pevnar 13 alone) to the experimental arm (Pevnar 13 plus lenalidomide).

16.11 Primary Endpoint:

The primary endpoint of this trial is the rate of response to the Pevnar 13 vaccine, which will be compared between the two arms. A response will be defined as a four-fold rise from pre-vaccine (day 15) to 28 days after immunization (day 43) for ≥ 2 of the 3 serotypes studied by opsonophagocytic activity (OPA) of antibodies from sera. Throughout Section 16.0, response will be considered synonymous with “success”, unless specified otherwise. All patients meeting the eligibility criteria who have signed a consent form and, received the Pevnar 13 vaccine will be evaluable for response, with the exception of patients who are determined to be a major treatment violation or flag.

16.2 Statistical Design:

16.21 Decision Rule:

It has been shown that CLL patients have poor response to vaccines. In previous studies, responses to the polysaccharide pneumococcal vaccine (Pneumovax) have been remarkably low, with responses ranging from 10-22%.^{13,14} Similar responses are expected with the Pevnar 13 vaccine. The addition of lenalidomide is expected to increase response rates to Pevnar 13 vaccine.

A randomized trial comparing the experimental arm (Pevnar 13 plus lenalidomide) against the control arm (Pevnar 13 alone) will be conducted as described by Rubinstein³⁴. We will enter 26 evaluable patients on each arm of the study using a 1:1 randomization scheme utilizing the Pocock and Simon dynamic allocation procedure³⁵, where patients are stratified based on age (<65 vs. ≥ 65), Rai stage (MBL or 0 vs. I), and previous Pneumovax (yes vs. no). A sample size of 26 patients per arm provides 80% power to detect an improvement in response rate from 10% to 30%, using a one-sided test at a significance level of 0.16 (EAST 6.2).

The z-score will be calculated for testing the null hypothesis that the difference of response rates between the two arms is equal to zero, based on the normal approximation with pooled variance of standardized test statistics.

16.211 Final Decision Rule: The final analysis will take place after all 52 evaluable patients have completed the response evaluation at 43 days.

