The response rates will be compared between the two arms using EAST6. If the response rate is higher in the experimental arm, where the z-score is greater than 0.988 (p-value < 0.162), this will be considered sufficient evidence that the experimental arm may be recommended for further testing in subsequent studies. Otherwise, we will conclude that there is not statistical evidence of superiority of the experimental regimen.

16.212 Over Accrual: If more than the target number of patients are accrued, the additional patients will not be used to evaluate the stopping rule or used in any decision making process. Analyses involving over accrued patients are discussed in Section 16.33.

16.22 Sample Size:

The randomized phase II study design to be used is fully described in section 16.21. A maximum of 52 evaluable patients (26 in each arm) will be accrued onto this phase II study unless undue toxicity is encountered. We anticipate accruing an additional 6 patients (3 in each arm) to account for ineligibility, cancellation, major treatment violation, or failure to receive the Prevnar 13vaccine. Maximum projected accrual is 58 patients.

16.23 Accrual Rate and Study Duration:

The anticipated accrual rate is approximately 3-4 patients per month. Therefore, the accrual period for this phase II study is expected to be about 1.5 years. The final analysis can begin approximately 1.75 years after the trial begins, i.e. as soon as the final patient accrued to this trial has completed the response evaluation at 43 days and data entry has been completed.

16.24 Power and Significance Level: Assuming that the responses are binomially distributed in each arm, the operating characteristics of the current design can be tabulated according to various true differences of the proportions, including the probabilities that the experimental regimen is superior to the control regimen.

If the true difference is proportions is	0	0.10	0.20	0.30
Then the probability of declaring that the experimental regimen warrants further studies is....	0.16	0.51	0.80	0.95

16.25 Other Considerations: Toxicity, quality/duration of response, and patterns of treatment failure observed in this study, as well as scientific discoveries or changes in standard care will be taken into account in any decision to terminate the study.

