16.321 Disease status by physical exam and complete blood counts will be evaluated in each patient. For CLL, each patient will be classified as CCR, CCRi, PR, SD, or PD per Section 11.2 at the time of the 6 week assessment of immune response. The distribution of disease status will be evaluated in each arm and will be summarized descriptively. Patients will be classified as responders (CCR, CCRi, PR) vs. non-responders (SD, PD). For MBL, patients will be classified as Not PD vs. PD. Differences in disease status response will be compared between the two arms using Fisher's exact test.

16.322 Time to treatment for progressive CLL will be defined as the time from the date of registration to the date of initiation of treatment for progressive CLL. The distribution of time to treatment will be estimated in each arm using the method of Kaplan-Meier. Time to treatment will be compared between the two arms using log-rank statistics.

16.323 Adverse Events: All eligible patients that have initiated treatment will be considered evaluable for assessing adverse event rate(s). Platelets and hemoglobin will be graded according to the Grading Scale for Hematologic Adverse Events in CLL Studies in Appendix IV. The maximum grade for each type of adverse event will be recorded for each patient, and frequency tables will be reviewed for each arm to determine

patterns. Additionally, the relationship of the adverse event(s) to the study treatment will be taken into consideration.

16.33 Correlative Analyses:

16.331 Pre-vaccination (day 15) and day 28 post-vaccination OPA GMTs for each serotype (4, 9V, 23F) will be reported in the vaccine and vaccine + lenalidomide groups. The fold-change in OPA GMT from baseline to 28 days post-vaccination will be evaluated for each serotype, where two-sample t-tests will be used to compare GMTs between the vaccine and vaccine + lenalidomide groups.

16.332 Pre-vaccination (day 15) and day 28 post-vaccination *Streptococcus pneumoniae* serotype specific IgG GMTs for each serotype (1, 3, 4, 5, 6B, 7F, 9V, 14, 18C, 19F, 19A, and 23) will be reported in the vaccine and vaccine + lenalidomide groups. The fold-change in quantitative IgG GMT from pre-vaccine (day 15) to 28 days post-vaccination will be evaluated for each serotype, where two-sample t-tests will be used to compare GMTs between the vaccine and vaccine + lenalidomide groups.

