16.333 Measures of global immune function including T-cell repertoire, T-cell immune synapse, serum immunoglobulin levels, and absolute numbers of T-cell and NK cells will be evaluated at both baseline and after 6 weeks of low dose lenalidomide. Values over time will be summarized graphically and descriptively. Changes from baseline to 6 weeks will be evaluated using paired t-tests. Two sample t-tests will be used to compare each measure between the vaccine and vaccine + lenalidomide groups.

16.34 Over Accrual: If more than the target number of patients are accrued, the additional patients will not be used to evaluate the stopping rule or used in any decision making processes; however, they will be included in final point estimates and confidence intervals.

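### The between-arm t-tests in 16.331–16.333 are unadjusted: 16.333 gives up precision, and the tested quantity is not fixed

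*Combined protocol and SAP*

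**What the plan says.** **OPA and IgG (16.331, 16.332).** Geometric mean titres are reported by arm at Day 15 and at 28 days after vaccination. For OPA, "The fold-change in OPA GMT from baseline to 28 days post-vaccination will be evaluated for each serotype", and then "two-sample t-tests will be used to compare GMTs between the vaccine and vaccine + lenalidomide groups". The IgG paragraph has the same form but names Day 15 as the reference. Objective 2.31 settles the reference for OPA: "fold-change from pre-vaccine (day 15) to 28 days post-vaccination in opsonophagocytic activity (OPA) GMT of antibodies from sera". Objective 2.32 does the same for IgG.

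**Immune function (16.333).** T-cell repertoire, T-cell synapse, serum immunoglobulins and cell counts are evaluated at baseline and at 6 weeks. Change over time is tested by paired t-tests. For the arms, "Two sample t-tests will be used to compare each measure between the vaccine and vaccine + lenalidomide groups".

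**What is available.** Section 4.0 (footnote 5) and the Section 14.1 table schedule research blood, including serum, at baseline, Day 15 and Day 43. Section 5.0 balances allocation on age, Rai stage and previous Pneumovax, and 6.21 adds the registering membership. No between-arm comparison in 16.33 uses a covariate.

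**The concern.** Three things are left on the table or left open.

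- **Precision in 16.333.** The text does not say whether the between-arm test is on the 6-week value or on the change from baseline. A 6-week-only test ignores baseline. A change score subtracts it in full, whatever the correlation. A model with baseline as a covariate has lower large-sample variance than either when 0 < r < 1 and the two variances are equal.
- **The tested quantity in 16.331–16.332.** The text evaluates fold change but then compares GMTs. It does not say whether the t-test is on Day 43 titres or on fold change, or that it is on the log scale.
- **The Day 15 reference.** In Arm A the Day 15 sample follows 14 days of lenalidomide (Section 7.1). Any drug effect on titre before vaccination is therefore subtracted out of the fold change. Registration is the only value taken before the drug.

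At stake is how informative the correlative results are with about 26 patients per arm.

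**Working it through.** **The plan's own figure.** The documents state power only for the binary primary endpoint: 26 per arm, 10% against 30%, one-sided 0.16, 80% power. With pooled variance, n = [0.9945 × √(2 × 0.2 × 0.8) + 0.8416 × √(0.09 + 0.21)]² / 0.2² = 26.2. The unpooled form gives 25.3. Power at 26 per arm is 0.506, 0.798 and 0.946 for differences of 0.10, 0.20 and 0.30, against 0.51, 0.80 and 0.95 in 16.24. The figure reproduces, but it says nothing about the 16.33 comparisons, for which no power, SD or correlation is given.

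**16.333: one common baseline.** Inputs: n = 26 per arm from 16.21 (assumed to apply here), equal variances at the two times (assumed), and r between registration and Day 43 (assumed). In units of the single-time variance:

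- Day 43 only: 1
- change score: 2(1 − r)
- adjusted for baseline: 1 − r²

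The adjusted variance is therefore (1 − r²) of the first and (1 − r²)/[2(1 − r)] = (1 + r)/2 of the second. The detectable difference at two-sided 0.05 (assumed) and 80% power is (1.960 + 0.842) × √(2/26) × √V = 0.777√V SD.

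| r | Variance: Day 43 only / change / adjusted | Adjusted is smaller than Day 43 only by | than change by | Detectable difference (SD), same order |
|---|---|---|---|---|
| 0.3 | 1 / 1.40 / 0.91 | 9% | 35% | 0.777 / 0.919 / 0.741 |
| 0.5 | 1 / 1.00 / 0.75 | 25% | 25% | 0.777 / 0.777 / 0.673 |
| 0.7 | 1 / 0.60 / 0.51 | 49% | 15% | 0.777 / 0.602 / 0.555 |

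On the standard-error scale, the reduction against Day 43 only is 4.6% at r = 0.3 (1 − √0.91) and 28.6% at r = 0.7 (1 − √0.51). Against the change score it is 19.4% (1 − √0.65) and 7.8% (1 − √0.85).

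**16.331–16.332: two different references.** The planned Day 15 log fold change has variance 2(1 − r), where r is the Day 15 to Day 43 correlation. A Day 43 model adjusted for registration has variance 1 − ρ², where ρ is the registration to Day 43 correlation. Two assumed patterns are equal correlations (ρ = r) and correlations that decay with time (ρ = r²).

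| r | Day 15 fold change, 2(1 − r) | Registration-adjusted, ρ = r | Registration-adjusted, ρ = r² |
|---|---|---|---|
| 0.3 | 1.40 | 0.91 | 0.99 |
| 0.5 | 1.00 | 0.75 | 0.94 |
| 0.7 | 0.60 | 0.51 | 0.76 |
| 0.8 | 0.40 | 0.36 | 0.59 |

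Under decay, the registration model has larger variance by 0.76/0.60 − 1 = 27% at r = 0.7 and by 0.59/0.40 − 1 = 48% at r = 0.8. A simulation at 26 per arm (8,000 trials per setting) showed the same pattern. At r = 0.5 under decay it found almost no gain (0.97 against 0.96).

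**Serum collection.** The Section 14.1 table has red-top serum at baseline, Day 15 and Day 43. The Appendix VI kit sheet has red-top tubes at baseline and Day 43 only. The Day 15 serum is needed for the fold change and for the primary endpoint.

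**The case against.** The case against is substantial.

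- **The go/no-go decision.** A reader might infer that these comparisons support it. They do not. Section 16.211 rests the decision only on the z-score for the binary OPA response. Sections 2.3 and 16.33 label these analyses correlative. This stands in full.
- **Baseline in 16.333.** A reader might infer that immune function ignores baseline altogether. It does not, because change is tested by paired t-tests. Those tests look at change over time and do not compare arms, so the gap in the between-arm test remains.
- **Carrying the percentages over to OPA and IgG.** The 15% to 35% figure needs the same baseline in both methods. The planned fold change uses Day 15, so replacing it with a registration-adjusted model could gain or lose precision. This stands.
- **Estimand.** Objectives 2.31 and 2.32 ask for the change from Day 15. A Day 43 model adjusted for registration also takes in any lenalidomide effect before vaccination. It answers a different question and should not displace the stated one. This stands.
- **Scale and factors.** A log scale is not obviously right for every 16.333 measure, such as percentage conjugation. Adjusting only for the three factors of Section 5.0 would miss the one added in 6.21. Both stand.

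What survives is the like-for-like gain in 16.333 and the unclear wording in 16.331–16.332.

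**Conclusion.** The point holds as an improvement to correlative analyses. It is not an error: the unadjusted t-tests are valid under randomisation, and the primary analysis and decision rule are unaffected.

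For 16.333 the gain is real but cannot be sized from the documents. For assumed r = 0.3 to 0.7 and equal variances, the large-sample variance falls by 9% to 49% against a Day 43-only test and by 35% to 15% against a change score. Estimating the baseline slope takes back roughly 2% of variance at this sample size.

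For 16.331–16.332 no precision gain over the Day 15 fold change is claimed. The need there is to state the tested quantity and scale and to use the randomisation factors. A registration-adjusted result is useful as a companion because Day 15 is after the start of lenalidomide in Arm A.

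A reader might also infer from the kit sheet that Day 15 serum will not be drawn. Sections 4.0 and 14.1 schedule it, so the documents support only that the passages conflict.

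**What to change.** 1. **16.333.** Replace the between-arm t-test with a linear model of the Day 43 value on arm, the registration value and the randomisation factors (age, Rai stage, previous Pneumovax and the registering membership of 6.21). Use the log scale only where it suits the measure. Report the adjusted difference or ratio with a 95% CI.
2. **16.331–16.332.** Keep the Day 15 fold change of objectives 2.31–2.32 as the lead estimate. State that the test is on log fold change, and add the randomisation factors. Replace the word baseline by Day 15 in 16.331, and in 14.22 where it means the pre-vaccine sample.
3. **Companion model.** Where registration serum is assayed, report alongside it the log Day 43 titre on arm, log registration titre and the same factors. Say that it includes any drug effect before vaccination. The sponsor should confirm that the assay is planned: 11.1 names only Day 15 and Day 43 for OPA, while 18.1 lists OPA and IgG forms among the initial materials.
4. **Appendix VI.** Reconcile its serum time points with the Section 14.1 table.

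The cost is wording in 16.33, 14.22 and Appendix VI, a little more analysis work and a few degrees of freedom. If membership means the three sites in 6.16, residual degrees of freedom go from 52 − 2 = 50 to 52 − 8 = 44 (intercept, arm, registration value, three binary factors, two for site). No new samples are needed. Item 3 adds assay cost only if registration serum is not already to be tested.

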16.35 Data & Safety Monitoring

16.351 The principal investigator(s) and the study statistician will review the study at least every quarter to identify accrual, adverse event, and any endpoint problems that might be developing. The Mayo Clinic Cancer Center (MCCC) Data Safety Monitoring Board (DSMB) is responsible for reviewing accrual and safety data for this trial at least twice a year, based on reports provided by the MCCC Statistical Office.

16.352 Adverse Event Stopping (applies to each arm independently): The stopping rule specified below is based on the knowledge available at study development. We note that the rule may be adjusted in the event of either (1) the study re-opening to accrual or (2) at any time during the conduct of the trial and in consideration of newly acquired information regarding the adverse event profile of the treatments under investigation.

The study team may choose to suspend accrual because of unexpected adverse event profiles that have not crossed the specified rule below.

Accrual will be temporarily suspended to both arms if at any time we observe events considered at least possibly related to study treatment (i.e. an adverse event with attribute specified as “possible,” “probable,” or “definite”) that satisfy either of the following:

- if 4 or more patients in the first 15 treated patients in either arm experience a grade 4 or higher non-hematologic adverse event at least possibly related to treatment.
- if after the first 15 patients have been treated, 25% of all patients in either arm experience a grade 4 or higher non-hematologic adverse event at least possibly related to treatment.
- Any grade 5 event related to treatment

We note that we will review grade 4 and 5 adverse events deemed “unrelated” or “unlikely to be related”, to verify their attribution and to monitor the emergence of a previously unrecognized treatment-related adverse event.

16.353 Enhanced Safety Monitoring Rule: If at any time after the first 12 patients have been treated on the experimental arm, the rate of grade 3 or 4 non-hematologic adverse events in the experimental arm is \geq 25% higher than the rate in the control arm, the study team will review the adverse events profile in each arm. Accrual may be temporarily suspended to evaluate the types of adverse events and the relation to study treatment.

16.4 Results Reporting on ClinicalTrials.gov: At study activation, this study will have been registered within the “ClinicalTrials.gov” website. The Primary and Secondary Endpoints along with other required information for this study will be reported on ClinicalTrials.gov. For purposes of timing of the Results Reporting, the initial estimated completion date for the Primary Endpoint of this study is 1.75 years after the study opens to accrual. The definition of “Primary Endpoint Completion Date” (PECD) for this study is at the time the last patient registered has completed the response evaluation at 43 days.

16.5 Inclusion of Women and Minorities

16.51 This study will be available to all eligible patients, regardless of race, gender, or ethnic origin.

16.52 There is no information currently available regarding differential effects of this regimen in subsets defined by race or gender, and there is no reason to expect such differences to exist. Therefore, although the planned analysis will, as always, look for differences in treatment effect based on racial and gender groupings, the sample size is not increased in order to provide additional power for subset analyses.

- 16.53 The geographical region served by Mayo, has a population which includes approximately 3% minorities. Based on prior Mayo studies involving similar disease sites, we expect about 3-5% of patients will be classified as minorities by race and about 30% of patients will be women. Expected sizes of racial by gender subsets are shown in the following table:

Accrual Targets			
Ethnic Category	Sex/Gender		
	Females	Males	Total
Hispanic or Latino	0	1	1
Not Hispanic or Latino	17	40	57
Ethnic Category: Total of all subjects	17	40	58
Racial Category			
American Indian or Alaskan Native	0	0	0
Asian	0	0	0
Black or African American	0	1	1
Native Hawaiian or other Pacific Islander	0	0	0
White	17	40	57
Racial Category: Total of all subjects	17	41	58

Ethnic Categories: **Hispanic or Latino** – a person of Cuban, Mexican, Puerto Rican, South or Central American, or other Spanish culture or origin, regardless of race. The term “Spanish origin” can also be used in addition to “Hispanic or Latino.”

Not Hispanic or Latino

Racial Categories: **American Indian or Alaskan Native** – a person having origins in any of the original peoples of North, Central, or South America, and who maintains tribal affiliations or community attachment.

Asian – a person having origins in any of the original peoples of the Far East, Southeast Asia, or the Indian subcontinent including, for example, Cambodia, China, India, Japan, Korea, Malaysia, Pakistan, the Philippine Islands, Thailand, and Vietnam. (Note: Individuals from the Philippine Islands have been recorded as Pacific Islanders in previous data collection strategies.)

Black or African American – a person having origins in any of the black racial groups of Africa. Terms such as “Haitian” or “Negro” can be used in addition to “Black or African American.”

Native Hawaiian or other Pacific Islander – a person having origins in any of the original peoples of Hawaii, Guam, Samoa, or other Pacific Islands.

White – a person having origins in any of the original peoples of Europe, the Middle East, or North Africa.

17.0 Pathology Considerations/Tissue Biospecimens: None.

18.0 Records and Data Collection Procedures

18.1 Submission Timetable

Initial Material(s)

CRF	Active-Monitoring Phase (Compliance with Test Schedule Section 4.0)
On-Study	≤ 2 weeks after registration
Adverse Event - Baseline	
Measurement - Baseline	
Research Blood Submission (see Section 14.0)	
Other Laboratory Results	
OPA Titers	
Quantitative IgG Levels	
FISH Results - Baseline	
Quantitative Flow Cytometry	
Immunophenotyping Reports including CD38, CD49d, and ZAP-70 ^{1, 2}	
IgVH Mutation Analysis Report ¹	
CLL FISH Report ¹	
End of Active Treatment/Cancel Notification	Submit ≤ 2 weeks after registration if withdrawal/refusal occurs prior to beginning protocol therapy

1. Submit copy of the report, Attention: [REDACTED].
2. For patients who previously had full flow immunophenotyping performed and at pre-study workup had limited repeat flow immunophenotyping, submit a copy of both reports.

Test Schedule Material(s)

CRF	Active-Monitoring Phase (Compliance with Test Schedule Section 4.0)		
	At each evaluation during treatment	At end of treatment	Observation
Evaluation/Treatment ²		X	
Evaluation/Observation ¹			X
Nadir/Adverse Event		X	X
Measurement		X	X
Research Blood Submission		X (see Section 14.0)	
Other Laboratory Results		X	
Interval Laboratory		X	
OPA Titers		X	
Quantitative IgG Levels		X	
Quantitative Flow Cytometry		X	
End of Active Treatment/Cancel Notification		X	
ADR/AER	At each occurrence (see Section 10.0)		

1. Complete at each evaluation during Observation (see Section 4.0).
2. Complete at each evaluation during Active Treatment (see Section 4.0).

Follow-up Material(s)

CRF	Event Monitoring Phase ¹				
	q. 6 months until PD or subsequent treatment for CLL ²	At PD or subsequent treatment for CLL ²	q. 12 mos. after PD or subsequent treatment for CLL	Death	New Primary
Event Monitoring	X	X	X	X	At each occurrence

1. If a patient is still alive 2 years after registration, no further follow-up is required.

NOTE: As of Addendum 4, Event monitoring will no longer be required

2. Submit copy of documentation of response or progression, Attention: [REDACTED].

